### **2.4.2 Prior or concomitant medications**

The prior and concomitant medications have been defined in [Section 2.1.2](#).

Medications will be summarized by randomized treatment group using mITT population according to the WHO-DD, considering the first digit of the anatomic and therapeutic category (ATC) class (anatomic category) and the first 3 digits of the ATC class (therapeutic category). All ATC codes corresponding to a medication will be summarized, and patients will be counted once in each ATC category (anatomic or therapeutic) linked to the medication. Therefore patients may be counted more than once for the same medication, but for different ATC category. Prior and concomitant medications will be summarized separately.

The table for prior medications will be sorted by decreasing frequency of ATC followed by all other therapeutic classes based on the overall incidence across treatment groups. In case of equal frequency regarding ATCs (anatomic or therapeutic categories), alphabetical order will be used.

The tables for concomitant medications will be sorted by decreasing frequency of ATC followed by all other therapeutic classes based on the incidence in olipudase alfa treatment group. In case of equal frequency regarding ATCs (anatomic or therapeutic categories), alphabetical order will be used.

Prohibited medications during the study, if used, will be provided as part of a data listing for major and critical protocol deviations.

### **2.4.3 Smoking and alcohol drinking**

Alcohol and tobacco usage data will be provided in listings.

## 2.4.4 Extent of investigational medicinal product exposure and compliance

The extent of IMP exposure and compliance will be assessed and summarized by randomized treatment group in mITT population ([Section 2.3.1.1](#)).

### 2.4.4.1 Extent of investigational medicinal product exposure

The extent of study drug exposure will be assessed by the duration of study drug exposure, and amount of dose received.

Study drug exposure for PAP is defined below:

For patients who did not initiate rescue therapy:

- Duration of study drug exposure for PAP = the first dose date in ETP (or 13 days after the last dose date in PAP if the patient is not continuing in ETP) – first dose date in PAP, regardless of unplanned intermittent discontinuations

For patients who had initiated rescue therapy during PAP:

- Duration of rescue therapy exposure in PAP = the first dose date in ETP (or the last dose date in PAP + 13 days if the patient is not continuing in ETP) – first rescue therapy dose date in PAP, regardless of unplanned intermittent discontinuations.
- Duration of study drug exposure for PAP before initiation of rescue therapy = the first rescue therapy dose date in PAP – first dose date in PAP, regardless of unplanned intermittent discontinuations.

Study drug exposure for PAP (before initiation of rescue therapy if any) will be summarized descriptively. In addition, duration of treatment exposure in PAP may be summarized categorically, eg, <14 weeks, <26 weeks, etc. Duration of olipudase alfa exposure after rescue initiation will also be summarized.

Cumulative study drug exposure of olipudase alfa is defined as follows:

- Duration of cumulative study drug exposure = disposition date of the study (or the cutoff date for database lock if the patients are still ongoing) – first dose date of olipudase alfa infusion in the study + 1, regardless of unplanned intermittent discontinuations.

Duration of cumulative study drug exposure will be summarized descriptively as well as categorically.

**Dose information** for PAP will be assessed by the following variables for patients who received any dose of olipudase alfa:

The cumulative dose for PAP is the sum of total amount of olipudase alfa in mg received in all infusions in PAP. Total amount of olipudase alfa in each infusion is obtained from the patient dose level in mg/kg multiplied by weight, adjusted for partial infusion. When the question on the eCRF “Was the total volume infused?” indicates “No” (ie, infusion was partial), eCRF does not collect the volume actually infused (to maintain blinding, the color of the liquid is covered from

view); this needs to be imputed from the infusion rate and infusion time as follows: if the infusion rate is xx ml/hour and the duration of that infusion was zz hour, then the volume infused is imputed as (xx times zz) ml. The sum of such individual infusion volume over different infusions within a visit will constitute the partial volume infused. If the resulting volume is greater than total volume prepared, it will be imputed as equal to total volume. In case of partial infusion, the total amount of olipudase alfa in the infusion is considered as proportional to the volume infused.

Total amount of olipudase alfa in each infusion is obtained from the patient dose level in mg/kg multiplied by weight, adjusted for partial infusion:

= Dose level (mg/kg) \* weight (kg) if no partial infusion

= Dose level (mg/kg) \* weight (kg) \* partial volume infused (mL) / Total volume prepared (ml) if partial infusion

Cumulative dose in PAP for each patient will be summarized. In addition, the number and percentage of patients for whom the target dose of 3 mg/kg was not achieved, and separately for those who reach target dose but have to reduce dose later for safety reasons will be provided.

Any incorrect dosing will be part of protocol deviations.

The cumulative dose of olipudase alfa over the entire study will be summarized.

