10.3.4 Handling of patients after permanent treatment discontinuation

Any patient who discontinues participating in the study will be contacted by the study investigator to obtain information about the reason(s) for discontinuation and collection of any potential AEs.

If possible, all tests and evaluations listed for the end of study/early discontinuation visit in [Section 1.2](#) are to be carried out within 2 weeks of the last study drug infusion. If a patient fails to return for the necessary visits, then every effort must be made to contact the patient, determine the reason(s) for discontinuation, and record the reason(s) on the e-CRF.

In all cases, the sponsor must be notified of all study terminations as soon as possible and the reason for and date of withdrawal from the study must be recorded in the e-CRF and in the patient's medical record.

In addition, since the primary study comparison is based on intent to treat principle using all randomized patients with any study treatment, missing data, especially the key study assessments during the PAP (12 months) may potentially lead to biased results and challenges in assessing the treatment effect of the study drug. Therefore, all efforts should be made to continue to follow the patients for primary and key secondary endpoints, after the temporary or permanent discontinuation of treatment, in addition to the standard post study safety follow up. If possible, at the minimum, patients should be assessed at their regularly scheduled Week 52 visit (or as close as possible to Week 52) if treatment discontinuation occurred prior to that visit.

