#### ***Handling of computation of treatment duration if investigational medicinal product end of treatment date is missing***

For the calculation of the treatment duration, the date of the last dose of study treatment is reported on the last infusion page in the eCRF.

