## 2.6.6 Statistical technical issues

A sensitivity analysis of the primary efficacy endpoints using a pattern mixture model and different imputations for values missing during the on-treatment period versus values missing after treatment discontinuation is planned. The description of the analysis refers to the DLco endpoint; differences in the implementation for the spleen volume and splenomegaly-related scores are noted. On-treatment period is defined as the time period between the start of first infusion of the study drug up to the day of last infusion in PAP +13 days for patients who did not continue in ETP, or up to the day before first infusion in ETP if the patient continued into ETP.

A pattern-mixture model sensitivity analysis of the percentage change in DLco (% predicted) from baseline to 52 weeks will be conducted, with a different imputation strategy applied for missing DLco values during the on-treatment period and missing DLco values after treatment discontinuation (ie, after the day of last infusion +13 days) based on the following assumptions:

- Patients within 13 days of their last IMP infusion would continue to show benefit from treatment similar to that observed at the scheduled time point. Therefore, DLco values missing during the on-treatment period will be considered “Missing At Random” and imputed using a model estimated using all samples collected on-treatment.
- Patients who stop taking their study treatment will no longer benefit from it in the future, and thus will tend to have DLco values returning to baseline. Thus DLco values missing after treatment discontinuation will be imputed based on a patient’s own baseline value.

Missing DLco values will be imputed 100 times to generate 100 complete data sets. The percent change from baseline to 52 weeks will be derived from observed and imputed DLco at this time point. The complete data sets will be analyzed using an ANCOVA model with treatment group, baseline DLco and baseline age as covariates. The results from the 100 analyses will be combined using Rubin’s formulae.

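### Cumulative olipudase alfa exposure runs to the study disposition date, with no stop at the last infusion for patients who end treatment permanently, unlike the SAP's other exposure rules

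*SAP*

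**What the plan says.** SAP 2.4.4.1 gives this formula: "Duration of cumulative study drug exposure = disposition date of the study", with the alternative end date "or the cutoff date for database lock if the patients are still ongoing", minus "first dose date of olipudase alfa infusion in the study + 1, regardless of unplanned intermittent discontinuations". The only interruptions it says it ignores are intermittent ones. It does not mention a permanent stop, and neither document defines the disposition date.

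Two other places in the SAP end the treated period differently:

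- PAP exposure in the same section ends at the first dose of the extension treatment period (ETP), "or 13 days after the last dose date in PAP if the patient is not continuing in ETP". The rule for rescue therapy exposure has the same 13-day end.
- The on-treatment period in SAP 2.6.6 runs "up to the day of last infusion in PAP +13 days for patients who did not continue in ETP".

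The date needed for a 13-day rule is collected. SAP 2.6.2 says that "the date of the last dose of study treatment is reported on the last infusion page in the eCRF".

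On follow-up after stopping drug, the documents disagree:

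- Protocol 10.3.4 asks that patients be followed for the primary and key secondary endpoints after permanent discontinuation, if possible with at least a Week 52 assessment.
- Protocol 10.4.2 continues observation to the end of the study after premature discontinuation.
- SAP 2.4.6.1.5 says that a patient who permanently stops treatment is withdrawn from the study.

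**The concern.** As written, all time between the last infusion and disposition counts as olipudase alfa exposure. A patient who stops drug early and stays in follow-up, as the protocol asks, is credited with the off-drug months. The same may apply to a patient who is off drug but still in the study at a cutoff, since the SAP does not say whether ongoing means in the study or on treatment.

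With about 36 randomized patients, one or two such cases could visibly move a summary of long-term exposure. The error can only lengthen exposure, and it is largest for those who stopped earliest and stayed longest. It could also place one patient in a short-duration category in the PAP table and a long one in the cumulative table, for the same drug and period.

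**Working it through.** The documents state no exposure figure, so there is none to reproduce. The check is date arithmetic on the SAP's formulas.

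**Inputs**

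- End date of cumulative exposure, and its +1: SAP 2.4.4.1.
- 13-day end after the last infusion: SAP 2.4.4.1 (PAP rule) and SAP 2.6.6.
- End-of-study or early discontinuation visit within 14 days of the last infusion, and safety call at about 30 to 37 days: SAP 1.4.
- Week 52 = 52 × 7 = 364 days after the first infusion.

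**Formulas**, with the first olipudase alfa infusion on day 0, the last on day L and disposition on day D:

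- Current cumulative rule: D − 0 + 1.
- 13-day rule with the same +1: (L + 13) − 0 + 1 = L + 14.
- Excess: (D + 1) − (L + 14) = D − L − 13.

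The PAP formula as printed has no +1. It gives L + 13, one day less than the comparator used here.

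**Case A: followed off drug to Week 52.** Assume an olipudase-arm patient whose disposition is recorded on day 364. The current rule gives 364 + 1 = 365 days whatever the value of L.

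| Last infusion | L (days) | Current rule | 13-day rule, same +1 | Excess | Ratio |
|---|---|---|---|---|---|
| Week 8 | 56 | 365 | 70 | 295 | 5.2 |
| Week 14 | 98 | 365 | 112 | 253 | 3.3 |
| Week 26 | 182 | 365 | 196 | 169 | 1.9 |
| Week 38 | 266 | 365 | 280 | 85 | 1.3 |

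For the Week 14 patient, the two formulas as printed give 98 + 13 = 111 days of PAP exposure and 365 days of cumulative exposure. One day of that gap is only the +1.

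**Case B: disposition soon after the last infusion.** With D = L + d, the excess is d − 13.

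- End-of-study visit at d = 14: 14 − 13 = 1 day.
- Safety call at d = 30 to 37: 30 − 13 = 17 to 37 − 13 = 24 days.

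For a patient with a last infusion at Week 104 (L = 728, 13-day rule 742 days), 24 days is 24/742 = 3.2%. At Week 260 (L = 1820, 1834 days) it is 24/1834 = 1.3%.

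**Who is affected.** Case A needs a patient who received olipudase alfa during the PAP (active arm, or rescued from placebo), stopped it and stayed in follow-up. The table applies to the active arm. A rescued patient starts later, so the total differs, but the excess formula is the same. A patient who stops on placebo and never receives olipudase alfa has no such exposure to overcount.

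**The case against.** The strongest reply is SAP 2.4.6.1.5. If a permanent stop means study withdrawal, disposition follows the last infusion closely and only Case B remains. Protocol 10.3.4 also qualifies the Week 52 assessment as something to do if possible. This stands as far as size goes: on these documents the large figures are conditional.

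It does not remove the point. SAP 2.4.6.1.5 conflicts with protocol 10.3.4 and 10.4.2, and with protocol 11.5.2.1, which keeps DLco values regardless of treatment discontinuation. The SAP itself expects off-drug data: SAP 2.6.6 excludes from its imputation input any DLco value obtained more than 13 days after the last infusion, and SAP 2.2 tabulates treatment discontinuation separately from status at last contact.

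Three further replies have force:

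- **Early stopping is visible elsewhere.** The PAP exposure table, cumulative dose in mg, percentage of infusions received, and discontinuations by reason would all show it.
- **A Week 8 stop is an extreme example.** Under protocol 6.1, a patient who escalates through Week 4 but cannot tolerate later doses ordinarily continues at a tolerated dose. Protocol 10.3.3 lists other reasons for stopping, but no frequency is given.
- **Time to disposition is not a bad denominator for every purpose.** The SAP 2.1.5 treatment epoch runs to the end of the study, so treatment-emergent adverse events (TEAEs) are counted over roughly that window. A denominator ending 13 days after the last infusion would not match that count.

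A reader might therefore infer that TEAE rates will be diluted. The documents do not support this: SAP 1.5 moves annualized rates to the integrated summary of safety, whose denominator is not given here.

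**Conclusion.** The cumulative exposure rule is wrong as written for patients who permanently stop drug. It counts off-drug time as exposure and departs, without a stated reason, from the 13-day end used in the same section and in SAP 2.6.6.

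The size depends on which follow-up passage is applied. With off-drug follow-up to Week 52, the excess is 295 days for a last infusion at Week 8, falling to 85 days at Week 38. If disposition follows the last infusion closely, it is about 1 day, or 17 to 24 days. Case A assumes that disposition is recorded at Week 52, and Case B that it is recorded at the end-of-study visit or the safety call. The documents settle neither, and they do not say how many patients would stop early and stay in follow-up.

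A reader might infer that the trial's reported exposure will be several times too long, or that its long-term safety base will be materially overstated. Neither follows. The fivefold ratio belongs to one early-stop example, and the other planned outputs show the early stop. Only a descriptive summary is affected: the efficacy tests and the cumulative mg dose do not use this variable. The change is worth making because it is cheap, but the trial's conclusions do not depend on it.

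**What to change.** Replace the cumulative exposure definition in SAP 2.4.4.1 with two cases:

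- **Treatment permanently discontinued or completed:** the earliest of (last olipudase alfa infusion date + 13 days), the disposition or death date, and the cutoff date, minus the first olipudase alfa infusion date, + 1.
- **Still on treatment at the cutoff, including temporarily interrupted:** cutoff date minus first olipudase alfa infusion date, + 1.

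Keeping disposition or death as a cap avoids crediting days after a patient has left or died. The second case keeps the SAP's treatment of intermittent gaps.

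In addition:

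- Apply one +1 convention to all exposure formulas in the section.
- Define the disposition date, and say whether ongoing means on treatment or in the study.
- Reconcile SAP 2.4.6.1.5 with protocol 10.3.4 and 10.4.2.
- Report time in study as a separate variable, so that any TEAE rate can use a denominator that matches its event window.

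The cost is a few lines of SAP text and one derivation from a date already in the eCRF. No new data are needed. Reported cumulative exposure becomes shorter for patients whose disposition or cutoff falls more than 13 days after a final infusion, and is otherwise unchanged.

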8.1.3 Dosing considerations

Dosing will be based on an individual patient's mass (ie, weight) as outlined in [Section 8.1.1](#). For patients with a body mass index (BMI) >30 , the dose will be based on the mass (in kilograms) corresponding to a BMI of 30 given the specific patient's height.

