##### ***Physical examination***

A complete physical examination will be performed during the screening period, before infusion at Day 1 and at every quarterly visit, and will include a neurological examination (mental status, cranial nerves, muscle strength, sensation, deep-tendon reflexes, and coordination) and an assessment of the patient's general appearance; skin; head, eyes, ears, nose, and throat; and examinations of lymph nodes, heart, lungs, abdomen, and extremities/joints.

An abbreviated physical examination of the patient's general appearance only will be performed before and after infusion at every infusion visit.

Patients will be assessed for weight at screening, every infusion visit during dose escalation (both PAP and ETP) and at quarterly visits. Height will be assessed at Screening and every yearly visit. Body mass index (BMI) will be calculated at the every visit that weight is measured, using the latest height and current weight available.

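### The SAP's cumulative-dose formula uses body weight without the BMI-30 limit applied to dosing, so it overstates the mg received for olipudase alfa infusions given while BMI is above 30

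*SAP*

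**What the plan says.** SAP 2.4.4.1 defines the summary measure as an amount received: "The cumulative dose for PAP is the sum of total amount of olipudase alfa in mg received in all infusions in PAP". It then gives the building block: "Total amount of olipudase alfa in each infusion is obtained from the patient dose level in mg/kg multiplied by weight", with an adjustment when an infusion is partial. A complete infusion counts as dose level (mg/kg) times weight (kg). A partial one is the same product times the ratio of volume infused to volume prepared, because "the total amount of olipudase alfa in the infusion is considered as proportional to the volume infused". The measure is reported for patients who received any olipudase alfa, per patient for the PAP and again over the entire study.

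Protocol 8.1.3 sets the weight on which the dose is prepared. The general rule is "Dosing will be based on an individual patient's mass (ie, weight) as outlined in" Section 8.1.1. For patients with BMI above 30, "the dose will be based on the mass (in kilograms) corresponding to a BMI of 30 given the specific patient's height".

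The SAP does not mention this limit. SAP 1.5, which lists differences from the protocol's statistical section, records a change of population for the exposure summary but nothing about weight.

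**The concern.** The SAP formula is meant to recover the mg that went into the patient. Above BMI 30 it multiplies the dose level by a larger weight than the one used to prepare the infusion, so it does not recover that amount. The error can only go upward, so it does not average out over infusions or patients. No inclusion or exclusion criterion removes patients with BMI above 30, and the protocol has a rule written for them.

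What is at stake is the accuracy of one planned exposure result. With 36 patients randomized 1:1, about 18 start on olipudase alfa, so a single affected patient could set the reported maximum.

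**Working it through.** The SAP states no cumulative-dose figure to reproduce. The one related count, 27 planned PAP infusions (SAP 2.4.4.2), does reproduce: Weeks 0 to 52 every 2 weeks gives 52/2 + 1 = 27.

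**Which weight the SAP means.** SAP 2.4.4.1 does not label the term. Elsewhere in the SAP, weight is the measured value. The spleen and liver multiples-of-normal formulas take it from the visit or the closest available one, and in the physical examination section "Body mass index (BMI) will be calculated at the every visit that weight is measured, using the latest height and current weight available". I therefore take it as measured weight.

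**Algebra.** Let D be the dose level, f the fraction of the volume infused, h the height in metres and W = BMI × h² the weight.

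- SAP amount = D × f × BMI × h²
- Amount under protocol 8.1.3 when BMI > 30 = D × f × 30 × h²
- Ratio = BMI/30

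Height, dose level and volume fraction cancel. At BMI 30 or below the two amounts agree.

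| BMI (illustrative) | Overstatement = BMI/30 − 1 |
|---|---|
| 30 or below | 0% |
| 31 | 3.3% |
| 32 | 6.7% |
| 35 | 16.7% |
| 40 | 33.3% |

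**In mg, for one patient.** Under protocol Table 1 with no missed, repeated or reduced dose, the PAP total is 0.1 + 0.3 + 0.3 + 0.6 + 0.6 + 1.0 + 2.0 = 4.9 mg/kg for Weeks 0 to 12, plus 20 × 3.0 = 60 mg/kg for Weeks 14 to 52. That makes 64.9 mg/kg. Assume a height of 1.65 m (h² = 2.7225) and a constant BMI of 35.

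- Measured weight: 35 × 2.7225 = 95.3 kg
- BMI-30 weight: 30 × 2.7225 = 81.7 kg
- One 3.0 mg/kg infusion: 285.9 mg by the SAP formula, 245.0 mg under the protocol rule
- PAP cumulative dose: 6184 mg by the SAP formula, 5301 mg under the protocol rule
- Ratio: 6184/5301 = 1.167

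**On a group mean, purely as illustration.** Suppose k of 18 patients have BMI 35 and all 18 truly received the same mg. The mean is then overstated by k × 16.7%/18: 0% for k = 0, 0.9% for k = 1 and 2.8% for k = 3. The documents give no value for k.

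**Where BMI/30 is only approximate.** The factor is exact when the weight entered in the SAP formula is the weight behind that dose. In the PAP after dose escalation, weight is scheduled only at Weeks 26, 38 and 52. The schedule footnotes allow a previous visit's weight when the current one is missing during escalation, and an earlier weight in the extension. If BMI moves across 30, only the infusions given above 30 are affected.

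**The case against.** The strongest reply is that this is an undefined term and not a wrong formula. SAP 2.4.4.1 sets out to measure the amount received, and where the SAP wants a visit's weight it says so, as in the organ-volume formulas. A programmer could read weight here as the weight used to prepare the infusion. The interactive response system assigns vials partly from patient weight (protocol 8.4) and preparation details sit in the pharmacy manual, so the variable feeding the exposure dataset cannot be seen.

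Part of this stands. The documents do not show which variable will be used, so the size is conditional on measured weight. But nothing in the SAP supports the dosing-weight reading: it has no such variable and makes no reference to the BMI rule. If that reading was intended, a sentence saying so is still needed.

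The limits on scope also stand. Placebo-only patients have no PAP cumulative dose. The per-infusion amount is an intermediate step, not a listed result. The number of affected patients could be zero.

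**Conclusion.** The point holds as a minor correction. As written, and with weight taken as measured weight, the SAP formula overstates the descriptive cumulative dose, for the PAP and for the entire study, by a factor of about BMI/30 for olipudase alfa infusions given while BMI is above 30. The effect on group summaries cannot be sized, because the documents give no BMI distribution.

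A reader might infer that exposure as a whole is misreported, or that the efficacy or safety comparisons are compromised. The documents do not support that. Duration of exposure comes from dates, compliance from counts of infusions, and the target-dose counts from the mg/kg level. None of the efficacy tests uses cumulative mg. A reader might also infer that patients receive too much drug. The issue lies in the SAP's reconstruction after the fact, not in the dosing rule.

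**What to change.** In SAP 2.4.4.1, define weight in both the full- and partial-infusion formulas as the weight actually used to calculate the dose under protocol 8.1.3:

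dosing weight = min(weight used for dosing at that infusion, 30 × height² in m²)

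The first term is carried forward from the last measurement where the protocol allows. If the mg prepared are recorded, use those. With this definition the overstatement is 0% at every BMI; the example above gives 5301 mg.

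The cost is a sentence in the SAP and minor programming. Height and weight are already collected, but weight is not scheduled at every infusion, so the carry-forward rule has to be written down too. No dose or clinical rule changes.
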